3.3. Primary Endpoint(s)

The primary endpoint is the percentage of infants within each trial arm whose pediatric clinician adhered to the guidelines regarding peanut introduction assessed after completion of either a 4- or 6-month WCC. The primary endpoint concerns only the peanut introduction recommendation by the treating pediatric clinician and not additional behavior by the treating allergist or by caregivers. The primary endpoint will be measured separately by risk category as follows:

[figure not shown]
- % of infants at *low risk for peanut allergy* whose pediatric clinician adhered to the guidelines for that infant.
- % of infants at *high risk for peanut allergy* whose pediatric clinician adhered to the guidelines for that infant.

Adherence will be determined as follows: Infants will be stratified into high- versus low-risk categories based on the presence of severe eczema and/or egg allergy. Egg allergy and eczema diagnoses will be obtained from the “problem list” and “encounter diagnosis” sections of the EHR. Severe eczema will be further identified by the presence of prescriptions for topical corticosteroids, calcineurin inhibitors or other anti-inflammatory agents and/or clinician documented eczema classification (i.e., use of word “severe” and lack of words “mild or moderate”) found in the encounter notes through natural language processing (NLP).

For high-risk infants, pediatric clinician adherence will be determined as indicated in **Figure 4** by:

1. Actions taken by the pediatric clinician (peanut sIgE testing, referral to an allergy specialist, or neither). The information on these actions will be obtained from laboratory test and referral orders entered into the EHR.
2. Peanut sIgE testing results, if applicable (negative when IgE <0.35 kUA/L versus positive when IgE ≥ 0.35 kU/L). The information on these results will be obtained from laboratory test results entered into the EHR.
3. Dietary peanut introduction recommendation (recommendation to introduce or no recommendation). This information will be obtained from mentions of peanut introduction extracted from the encounter note using NLP (if sIgE ordered). If the information is absent from these sources, other sources will be utilized (i.e., parent- caregiver surveys and/or pediatric clinician surveys) to complement EHR data.

For low-risk infants, pediatric clinician adherence will be determined based on whether a recommendation for dietary peanut introduction was given. This information will be obtained from pediatric clinician notes made in the anticipatory guidance section using NLP. If the information is absent from these sources, other sources will be utilized (i.e., caregiver surveys) to complement EHR data.

Figure 4. Pediatric Clinician Adherence

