3.2. Description of Study Design

[figure not shown]
This study is a two-arm, cluster-randomized, controlled clinical trial. A minimum of 30 pediatric practice sites will be randomized to the iREACH intervention arm or to the control arm (**Figure 3**). All pediatric clinicians within each participating practice (n≈200 total) will be assigned to the arm to which their practice is randomized. Pediatric clinicians in the intervention arm will 1) receive the iREACH education module, 2) have the iREACH CDS tool integrated into the EHR templates for use at the 4-, 6-, 9-, 12-month WCC, and 3) will be reminded by EHR-embedded prompts at the 9-month WCC to ask caregivers whether peanuts were introduced and tolerated.

No study procedures will be implemented in the non-intervention, control practices, and their pediatric clinicians will not receive extra PPA Guidelines education, nor will any EHR modifications be made in their practices to support adherence to PPA guidelines. The trial will be conducted over an 18-month period. During this time, approximately 500 high-risk infants and 10,000 low-risk infants are expected to be seen for 4- and 6-month WCC. The primary outcome, pediatric clinician adherence to the PPA Guidelines, will be assessed using EHR data for each infant following the 6-month WCC.

Data for the secondary outcome will be obtained by a combination of EHR data extracted after the infant's 6-month WCC and data collected from caregivers. EHR data extraction will be performed to obtain data from the infant's 9-, 12-, 15-, 18-, 24-month WCC and any sick visits and allergist progress notes entered from 4-30 months of age. Caregivers' data will be collected via surveys of caregivers of children seen for 4- or 6-month WCC visits during the study period. Caregivers will be recruited and asked to provide informed consent at the time of the child's first birthday and questions will be asked to determine the incidence of peanut allergy. A follow-up survey will be sent to caregivers after the child's second birthday.

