3.6. Stratification, Randomization, and Blinding/Masking

Randomization will be accomplished through a password-protected, web-based, randomized system maintained by the Statistical and Data Coordinating Center. Practices will be randomized to intervention using a random number generator. Randomization will be stratified by size of the practice site, so that large volume practices are randomized to intervention separately from practices with fewer annual patients. Neither the control arm practice sites nor intervention sites will be blinded to their trial arm status.

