5.5. Potential Benefits

1. The iREACH intervention may improve the clinical decision making process of pediatric clinicians around peanut allergy risk assessment and counseling of caregivers and may lead to increased implementation of guidelines-based peanut product introduction.
2. If the intervention improves adherence to the PPA Guidelines, the following benefits may be seen:
 - a. Improved identification of infants at risk for peanut allergy by pediatric clinicians.
 - b. Prevention of unnecessary referrals to allergy specialists for infants at low-risk for peanut allergy.
 - c. Reduction in allergic reactions to peanut introduction in the home setting through improved identification of infants at risk for allergic reactions.
 - d. Improved confidence of caregivers regarding peanut introduction for prevention of peanut allergy.
 - e. Reduction in the incidence of peanut allergy in children.

6. Investigational Agent /Device/Intervention

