6.1. Investigational Agents/Devices/Interventions

6.1.1. Investigational Intervention: Intervention to Reduce Early (Peanut) Allergy in Children (iREACH)

The iREACH intervention consists of **A) an education module** about the PPA Guidelines and the research on which the guidelines were based; **B) an EHR-integrated CDS tool** in the 4- and 6-month WCC templates to support pediatric clinician decision-making around 1) proper triage of infants into peanut allergy risk categories, 2) allergy testing and interpretation and/or allergist referral for high-risk infants, and 3) caregivers counseling on peanut introduction including educational materials for families

and a minor addition to the anticipatory guidance section of the note template to facilitate documentation of PPA Guidelines discussion; and **C) follow-up prompts** in the 9- and 12-month WCC templates guiding pediatric clinicians to ask caregivers about inclusion of peanut products in their child's diet. The components of the intervention are detailed below:

A. Education Module: Text- and video-based educational materials covering the PPA Guidelines, the research on which the guidelines were based, and instructions for using the iREACH CDS tool will be delivered as an online module. Pre-and post-test knowledge surveys will be embedded into the module and permits monitoring of provider compliance with the assigned training. Key study personnel will be available via email, phone, or in-person to answer any questions that arise after completion of the educational module posttests.

B. CDS Tool: A multi-component tool within the EHR that includes the following:

- a. *A Best Practice Advisory (BPA)* will be triggered at 4- and 6-month well child visits to remind pediatric clinicians to evaluate child for peanut product introduction.
- b. *A Smart List* within note template to remind pediatric clinicians to assess the infant for conditions that would classify the infant as high-risk for PA (i.e., egg allergy or severe eczema).
- c. *A Smart Set* (order set) to guide the pediatric clinician in choosing peanut sIgE or allergist referral based upon PA risk status. The pediatric clinician selects orders based upon their assessment of PA risk. This Smart Set includes the option to print out a caregiver educational handout to assist with caregiver counseling on peanut product introduction.

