8.3. Timeline for Study Activities

Study activities will begin with practice randomization and continue for 18 months of observation.

During the 18-month observation period, all infants that will be seen by pediatric clinicians in participant practices for at least one 4- or 6-month WCC will be considered eligible for EHR data extraction, as long as they (and their caregivers) fulfill inclusion/exclusion criteria. During this period, EHR data will be extracted as described above (Table 8.2). Additional study activities related to the pediatric clinicians that will take place during the same period are described in Table 8.5.1.

For each study infant, information will be obtained through EHR until age 30 months. In addition, activities related to the infant caregivers will take place at 11, 12 and 24 months of the infant's age, as described in Table 8.5.2.

| Table 8.5.1. Schedule of Activities-Practice Sites, Pediatric Clinicians | 18-Month Study Observation Period | | |
|---|--|---------------|------------|
| | Beginning | Middle | End |
| PRACTICES | | | |
| Randomization of Practice Sites | X | | |
| INTERVENTION ARM PEDIATRIC CLINICIANS | | | |
| Pediatric Clinician Informed Consent | X | | |
| Pediatric Clinician Characteristics Questionnaire | X | | |
| Pediatric Clinician Knowledge Attitudes Barriers Facilitators Survey #1 | X | | |
| Pediatric Clinician Knowledge Attitudes Barriers Facilitators Survey #2 | | | X |
| Pediatric Clinician Knowledge Attitudes Barriers Facilitators Survey #3 | | | X |
| CONTROL ARM PEDIATRIC CLINICIANS | | | |
| Obtain Pediatric Clinician Informed Consent | | | X |
| Pediatric Clinician Characteristics Questionnaire | | | X |
| Pediatric Clinician Knowledge Attitudes Barriers Facilitators Survey | | | X |

| Table 8.5.2. Schedule of Activities-Caregivers | Age of Infant | | |
|--|-------------------------|-------------------------|---|
| | Around 12-months | Around 24-months | |
| CAREGIVERS | | | |
| Caregiver Opt-out Letter (if needed based on recruitment method) | | X | |
| Caregiver Informed Consent and Consent to Link Survey with | | X | X |
| Caregiver Characteristics Questionnaire | | X | X |
| Caregiver Feeding, Outcomes Attitudes, Barriers, Facilitators | | X | X |
| Caregiver Account of Clinician Peanut Recommendations, Testing and Introduction Survey | | X | |
| Caregiver Stress, Quality of Life | | X | X |

| | | | |
|--|--|---|---|
| Infant Food Frequency Questionnaire | | X | X |
|--|--|---|---|

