13.4.2 Primary Analysis of Primary Endpoint(s)

The primary endpoint is the percentage of infants in the PEDI sample within each trial arm whose pediatric clinician adhered to the guidelines regarding peanut introduction. The primary

endpoint concerns peanut introduction recommendation by the treating pediatric clinician only and not additional behavior by the treating allergist or by caregivers.

The primary endpoint will be computed using EHR data from the 4-month and 6-month WCCs as follows:

For low-risk infants:

- Adherence is achieved if the pediatric clinician recommends introduction of peanut products.
- Non-adherence is achieved if the pediatric clinician fails to recommend introduction.

For high-risk infants, adherence is assessed through three routes. A pediatric clinician is adherent if:

- The pediatric clinician does not order an sIgE test and refers the infant to an allergist.
- The pediatric clinician does order an sIgE test, the result is ≤ 0.35 , and the pediatric clinician recommends introduction.
- The pediatric clinician does order an sIgE test, the result is > 0.35 , and the pediatric clinician refers the infant to an allergist.

A pediatric clinician is non-adherent if:

- The pediatric clinician does not order an sIgE test and does not refer the infant to an allergist.
- The pediatric clinician does order an sIgE test, the result is ≤ 0.35 , and the pediatric clinician fails to recommend introduction.
- The pediatric clinician does order an sIgE test, the result is > 0.35 , and the pediatric clinician does not refer the infant to an allergist.

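### Risk group is read from charting made after randomisation, which iREACH prompts in one arm only, and no planned adherence or peanut allergy comparison is free of it

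*Combined protocol and SAP*

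**What the plan says.** **Timing.** Section 8.3: "Study activities will begin with practice randomization and continue for 18 months of observation". Section 3.6: "Randomization will be stratified by size of the practice site". Infant risk is not a stratification factor.

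**Label.** Section 3.3: "Infants will be stratified into high- versus low-risk categories based on the presence of severe eczema and/or egg allergy". The sources are the problem list, encounter diagnoses, anti-inflammatory prescriptions and severity words found in encounter notes by language processing. No date limit is given. Section 13.4.2 adds: "The primary endpoint will be computed using EHR data from the 4-month and 6-month WCCs".

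**What differs by arm.** Section 6.1.1 gives intervention clinicians an education module and, at the 4- and 6-month visits, a Smart List "within note template to remind pediatric clinicians to assess the infant for conditions that would classify the infant as high-risk for PA". Section 8.2.3 places the training shortly after enrolment. For control practices, section 3.2 says "nor will any EHR modifications be made in their practices to support adherence to PPA guidelines". Section 5.5 lists as a possible benefit, if adherence improves: "Improved identification of infants at risk for peanut allergy by pediatric clinicians".

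**Where the label is used.**
- Sections 13.4.2 and 13.4.4 analyse clinician adherence and peanut allergy separately by risk group.
- The pooled versions (13.4.3, 13.4.4) add risk group and its interaction with arm.
- Allergist adherence is for high-risk infants only, and clinician and caregiver adherence are scored by different rules in each risk group (13.4.2, 13.4.5).
- Section 13.4.6 will summarise the components of risk status and compare them across analysis samples. It does not say by arm.

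**The concern.** A subgroup can be compared between randomised arms without selection bias when membership is fixed before randomisation, or is recorded in a way that the intervention cannot influence. Here membership depends on what clinicians write and order after randomisation, and helping them identify high-risk infants is one of the tool's purposes. If it works, the infants called high-risk in the intervention arm may differ in kind from those called high-risk under usual care, and the low-risk groups differ by what was taken out of them.

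Both primary comparisons and both secondary comparisons would then contrast differently selected infants. Adjusting for the label does not help, because the label is the affected variable. No planned adherence or allergy comparison is free of it, so a reader of the final report could not judge whether it mattered.

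**Working it through.** **Inputs.** Section 13.7: at least 30 practices, with 17 high-risk and 333 low-risk infants each; ICC 0.07 (adherence) and 0.02 (peanut allergy); average adherence 0.50; allergy incidence 13.8% (high-risk) and 1.5% (low-risk); type 1 error 0.05. Allocation is 1:1 (section 13.3). Per arm: 15 practices and 15 × 350 = 5,250 infants; p = 17/350 = 4.86% charted high-risk, or 255.

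**The plan's own power.** Design effect = 1 + (m − 1) × ICC.
- High-risk: 1 + 16 × 0.07 = 2.12, so 255/2.12 = 120.3 effective infants per arm; 41% vs 59% gives 80.1% power.
- Low-risk: 1 + 332 × 0.07 = 24.24, so 4,995/24.24 = 206.1; 43% vs 57% gives 81.4%.

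The stated 18 and 14 points reproduce.

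**Illustrations.** Charting rates, adherence levels and the added infants' incidence are assumptions; there is no true effect. False rejection is for a two-sided 5% z-test with variance P(1 − P)[1 + (m − 1) × ICC]/n per arm, m = n/15.

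*A. High-risk allergy, over-charting.* iREACH also charts a fraction g of low-risk infants as high-risk, with incidence i. Its high-risk incidence is [p × 13.8% + (1 − p) × g × i] / [p + (1 − p) × g]. For g = 1%, i = 1.5%: (0.006703 + 0.000143)/0.05809 = 11.8%. Shift below 13.8% (false rejection):

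| i | g = 0.5% | g = 1% | g = 2% |
|---|---|---|---|
| 1.5% | 1.1 points (6%) | 2.0 (9%) | 3.5 (20%) |
| 5% | 0.8 (6%) | 1.4 (7%) | 2.5 (12%) |
| 8% | 0.5 (5%) | 1.0 (6%) | 1.6 (8%) |
| 13.8% | 0 (5%) | 0 (5%) | 0 (5%) |

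The last row also covers fuller charting that finds infants at the same risk.

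*B. High-risk adherence, fuller charting.* Take 255 per arm as truly high-risk. Controls chart a share c0 and iREACH 90%; adherence is 60% in infants charted anyway and a in the extra ones. iREACH reads [c0 × 0.60 + (0.9 − c0) × a]/0.9 against 60%.
- c0 = 0.7: (0.42 + 0.04)/0.9 = 51% for a = 0.2 (false rejection 26%); (0.42 + 0.16)/0.9 = 64% for a = 0.8 (10%).
- c0 = 0.8: 56% (10%) or 62% (6%).

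*C. Low-risk allergy, fuller charting.* iREACH charts all of a true 4.86% and controls chart f. Control low-risk incidence is [(p − f) × 13.8% + (1 − p) × 1.5%]/(1 − f). For f = 4%, 3%, 2% it is 1.61%, 1.74%, 1.86% against 1.50%: 0.11, 0.24 and 0.36 points (5.3%, 6.3%, 8.0%).

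*D. Low-risk adherence.* Charting as in C, adherence 50%, and the uncharted infants all adherent or all non-adherent: the shift is 0.5 × (p − f)/(1 − f) = 0.4, 1.0 and 1.5 points (false rejection at most 6.0%).

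**An allergy comparison without the label.** All-infant incidence = 0.0486 × 13.8% + 0.9514 × 1.5% = 2.10%. Design effect 1 + 349 × 0.02 = 7.98; 5,250/7.98 = 658 effective infants per arm. 2.10% vs 0.39% gives 80% power, so about 1.7 points is detectable.

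**The case against.** One algorithm serves both arms, and the guidelines are risk-specific, so analysing by risk group is natural. The direct prompt is also narrow. It asks for an assessment; it does not ask for eczema prescriptions or problem-list codes, which supply much of the label. Some entries will predate the visit. Whether template text can reach the severity search depends on code and a data dictionary that are not in the document. The bias may be nil.

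All of this stands as a limit on size. It does not remove the structure: nothing restricts the label to earlier entries, and training can change charting outside the prompted fields.

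A reader might take the pilot in section 1.4 as proof that the tool changes charting: 8/151 (5.3%) high-risk in the iREACH clinic against 1/312 (0.3%) in the other, Fisher p = 0.0007. It is not proof. These were two non-randomised clinics with nine high-risk infants in all, and case mix could explain the gap.

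**Conclusion.** The concern holds as a structural weakness that the plan neither measures nor works around, and it should be fixed. The between-arm clinician survey comparisons in 13.4.5 are unaffected, but the analysis there relating each clinician's proportion adherent to survey answers inherits the label.

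The illustrations rest on assumed charting and show what could happen, not what will. High-risk allergy moves by 0 to 3.5 points (false rejection 5% to 20%), high-risk adherence by −9 to +4 points, and low-risk adherence by at most about 1.5 points against a 14-point target.

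Two stronger readings are not supported:
- *That the design favours iREACH.* Direction cannot be derived. The largest adherence shift, 51% vs 60%, would mask a benefit.
- *That allergy is equally exposed in both strata relative to the detectable differences.* This leans on the 0.98 points given for low-risk infants in 13.7, which its own arm proportions contradict (1.50 − 0.11 = 1.39). Those proportions give about 80% power; 0.98 points from 1.50% gives about 43%. The shifts also come from different assumed mechanisms.

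**What to change.** Keep the current definition as primary.

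1. **In 13.4.4**, add a comparison of peanut allergy by arm in all infants, with no risk-group term. Describe it as free of risk-group selection but not of differences in ascertainment: only intervention templates prompt charting of introduction and tolerance at 9 and 12 months (6.1.1), and pediatric clinician diagnoses count toward the endpoint (3.4). With about 1.7 points detectable, it is a check and not a replacement.
2. **In 13.4.6**, report by arm the percent charted high-risk and the risk components already planned, with confidence intervals that allow for clustering. Qualify stratum-specific conclusions accordingly, noting that chance imbalance is possible with 15 practices per arm.
3. **Optional, chiefly for peanut allergy:** a sensitivity analysis with risk taken only from problem-list entries and medication orders dated before the first study visit, excluding decision-support and template text. Describe it as reducing the exposure, not removing it, since most such entries still follow randomisation and training. It drops note wording, and it depends on orders from before the 4-month visit being extracted, which 8.2.2 does not confirm. For adherence it would be supportive at most. Infants first identified at the visit would fall under the low-risk rule, "Non-adherence is achieved if the pediatric clinician fails to recommend introduction", so a test or referral without that recommendation would count as non-adherent.

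An all-infant adherence comparison would not help, because adherence is itself scored by charted risk.

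Items 1 and 2 cost SAP wording and a little programming. Item 3 can use the problem-entry and order dates listed in Table 8.2, but would class fewer infants as high-risk; how many is unknown.

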3.4. Secondary Endpoint(s)

The secondary endpoint is the incidence of peanut allergy by age 2.5 years and is assessed through a combination of parent survey data and extracted EHR data. Secondary endpoints will be measured separately by risk category as follows:

- % of infants at low risk for peanut allergy who developed peanut allergy by age 2.5.
- % of infants at high risk for peanut allergy who developed peanut allergy by age 2.5.

Peanut allergy determination will follow a hierarchy based on the source of information (tiers). This hierarchy will offer the first level of diagnostic confidence. If the diagnosis was made by an allergist, we will consider this as the highest confidence for peanut allergy (Tier 1). If the diagnosis was made by a pediatric clinician, we will consider it as Tier 2 and if it was only based on information from a caregiver (through the surveys that we will conduct at when the child is age 12 and 24 months), Tier 3.

Within each tier, there are diagnostic categories that reflect a decision algorithm based on tier-specific data. The diagnostic categories are as follows:

- Confirmed Diagnosis
- Convincing Diagnosis
- Questionable Diagnosis
- No Peanut Allergy (PA)

[figure not shown]
This double system approach (tiers and diagnostic categories) will offer substantial transparency for diagnosis and will allow us to evaluate whether the impact of our intervention can be evidenced at a particular level of diagnostic certainty. The details of the algorithm can be found in the Manual of Procedures.

